- Myocardial infarction within the past 6 months (exclusions applies only to CPM testing)
- History of Raynaud's syndrome, active vasculitis, or peripheral vascular disease. (exclusions applies only to CPM testing)
- History of lymphedema, Takayasu's arteritis, or arteriovenous fistula for hemodialysis in both arms (exclusion applies only to CPM testing)
- Mini-mental state examination (MMSE) score < 24 (only applies to optional brain function testing testing)

3c. Screening Process

Overview of the screening process

[figure not shown]

Figure 2: Screening procedures

Participants, recruited by Trialfacts and other recruitment efforts, who pass the online pre-screening form will be given a telephone screening call by a research assistant. This phone call will provide the participant detailed information about the study including goals, interventions, and participant expectation in terms of intervention and research visits. This call will also be used as an opportunity to ask clarifying questions to review eligibility of the participant. During this phone call, participants who are interested in participating in the study will undergo e-consenting procedures through REDCap database. Once the participant has electronically signed the consent form, the research assistant will sign the consent form. A copy of the consent form with both the participant and the research assistant's signature will be sent to the participant's email. A copy of the signed consent form will be saved on the lab's server for study documentation.

4. Research Visits

The proposed study is an 18-week feasibility study. There are a total of four remote research visits. These include a remote baseline (week 0), post-intervention (week 8), follow-up (week 14), and individual interviews at week 8 only for participants in the mindful exercise group. Participants who opt-in for the in-person visits will make two in-person visits to Boston University. Apart from these research visits, participants will be administered a weekly survey that will document their pain and activity levels. The weekly survey will be administered throughout the 18-week study period. An overview of these visits along with compensation for each visit is shown in the table below.

Table 4. Overview of research visits

Visit	Week	Type of visit	Duration	Payment
Remote Baseline Visit	2-4 weeks before start of treatment	Remote	30 min	\$25

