- 3. 6-minute walk test (6MWT): Walking for 6 minutes (x1)
- 4. Sit to stand test: sit to stand from chair (x5)

Quantitative Sensory Testing (QST): This series of tests will allow us to measure pain sensitivity: pressure-pain threshold (PPT), temporal summation, and conditioned pain modulation.

Strength testing: We will measure the strength of their leg muscles by asking them to provide maximal muscle contraction against a resistance. This testing will be done using a dynamometer commonly used in physical therapy clinics.

Brain function test: Participants will first complete the Mini-Mental State Examination survey (MMSE) to determine eligibility for the optional brain function testing using fNIRS. Only participants who meet the MMSE criteria and agree to brain function testing will undergo these procedures. Participants will wear a wireless fNIRS device (NIRSport, NIRx, Medical Technologies) with 30 channels. 10 sources and 12 detectors over their scalp surface of bilateral prefrontal cortex (i.e., forehead). Four surface electromyography sensors will be attached around their knee joint muscles. For the test, participants will wear the device and sensors and complete walking, dual-task walking, step-up, and sub-maximal strengthening exercise to investigate the cortical function and movement patterns during these activities.

4c. Remote Randomization and Telehealth Training Visit

After the baseline visit testing procedures are completed, participants will meet with a research assistant in a remote randomization and telehealth training visit. At the visit, participant attendance and fidelity of the telehealth training visit will be documented in "Telehealth Training Visit Tracking" form on REDCap.

Randomization procedures

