A randomization list will be generated by study biostatistician and will be stratified by sex. This provides an assignment that the study staff has no control over the randomization process and that each participant has an equal chance of being assigned to either group. These group assignments will be pre-specified and placed in sealed envelopes unmarked except for an envelope number (TEMPO1## or TEMPO2##) on the outside. Envelopes with numbers starting with the number 1 (e.g., TEMPO1##) will be for male participants and those starting with the number 2 TEMPO 2## will be for female participants. For participants who opted-in for the in-person baseline visit, the randomization procedures will occur inperson after the baseline data collection procedures have been completed.

Below is a script that the research assistant will use for the randomization procedures

4d. Post-Intervention (Week 8) Visit

The weekly attendance of the participants will be tracked on an Attendance Survey on REDCap. The completion of the 8th session will trigger the ASI for the post-intervention remote surveys. Participants will receive a total of 15 surveys, including self-reported pain, function, and psychological measures collected at baseline and feedback and satisfaction surveys. Those who opted in for the in-person baseline visit will be invited for the in-person post-intervention visit.

4e. Follow-up (Week 14) Surveys

Six weeks after the end of the 8-week intervention, participants will be administered six surveys related to their knee pain, function, perceived impression of change, and psychological measures.

4f. Weekly (Week 1-14) Surveys

All participants will be administered a short weekly survey starting from the start of the intervention (week 1) to the follow-up period (week 14). This weekly survey will include a question related to pain in a specific activity selected at baseline and will also include home exercise, physical activity, and medication log. For those assigned to the mindful exercise group, additional questions related to mindfulness and mindful exercise log will be included. The weekly survey will be administered by email using automated survey reminders in REDCap.

4g. Individual Interviews (Week 8)

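### A biostatistician's list secures the sequence but not its release: concealment from sealed envelopes run by the research assistant role is not assured as shown, and release through REDCap would be a cheap improvement

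*Combined protocol and SAP*

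**What the plan says.** Section 4c (Randomization procedures) covers who makes the sequence: "A randomization list will be generated by study biostatistician and will be stratified by sex". From this it draws the assurance at issue: "This provides an assignment that the study staff has no control over the randomization process". It also describes allocation to the two arms as equally likely.

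The same section gives the release mechanism. Assignments are fixed in advance and "placed in sealed envelopes unmarked except for an envelope number (TEMPO1## or TEMPO2##) on the outside", with one number series for men and the other for women. The person who runs the step is identified by role: "Below is a script that the research assistant will use for the randomization procedures". The script itself does not appear in the supplied text; section 4d follows directly.

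Two other places give the roles around that step. In section 3c (Screening Process), candidates "who pass the online pre-screening form will be given a telephone screening call by a research assistant". That call is also used to review eligibility and to take e-consent in REDCap, which the research assistant countersigns. In section 4c, once baseline testing is done, "participants will meet with a research assistant in a remote randomization and telehealth training visit". Participants who opted in to the in-person baseline visit are instead randomised in person after their baseline data have been collected.

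**The concern.** Generating an unpredictable sequence and concealing the next assignment are separate safeguards. Section 4c names the first and claims the benefit of both. Whoever opens the envelopes has the practical opportunity to open one early, pass over one, or match one to a particular participant. Who wrote the list does not close that opportunity. Here the opener belongs to the role that has already judged eligibility and taken consent, and the text shown names no independent person at the point of release.

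The setting adds to this in three ways:

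- At a remote visit the participant is elsewhere and cannot handle the envelope. The REDCap form that section 4c names for that visit is described as recording attendance and training fidelity; allocation is not mentioned.
- Section 5b has recruitment and randomisation continuing while wave 1 is being treated, so an assignment seen ahead of time could influence later enrolment.
- The arms are plainly different to everyone involved: sessions last one hour in one arm (section 5b.1) and about two in the other (section 5b.2). Most outcomes are self-reported.

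At stake are the between-group differences in patient-reported outcomes that section 7 will report with 95% confidence intervals, and any comparison of attendance or retention by arm. Recruitment is measured before allocation and is not affected.

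**Working it through.** The documents give no figure on this point to reproduce, and no power calculation. The check is a comparison of texts, followed by one illustrative calculation.

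**Steps and roles**

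| Step | Who, as stated | Where |
|---|---|---|
| Generate list, stratified by sex | Study biostatistician | 4c |
| Screening call, eligibility review | A research assistant | 3c |
| Countersign consent | The research assistant | 3c |
| Fill and hold envelopes | Not stated | 4c |
| Meet the participant for randomisation, use the script | A research assistant | 4c |
| Opacity, opening order within sex, identifier recorded before opening, opening log | Not in the text shown; may be in the script | 4c |

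The assurance in section 4c follows from the first row only. The rows that govern release are either assigned to the research assistant role or not visible. Consent and baseline precede allocation, so steering would need an envelope to be opened early or out of order. The text shown does not exclude that.

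**Sensitivity of a trial this small**

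Inputs: 40 participants in total (study overview) and equal chance of either arm (4c). From these I assume 20 per arm with complete data. The gap *d* between two swapped participants, in SD units, and the number of swaps *k*, all in the same direction, are also assumptions.

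- Swapping one pair raises one arm mean by *d*/20 and lowers the other by *d*/20, so the difference moves by 2*d*/20. At *d* = 1 this is 2 × 1/20 = 0.10 SD.
- Standard error of the difference: √(1/20 + 1/20) = √0.10 = 0.316 SD.
- Ratio for one swap: 0.10/0.316 = 0.32.

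| Swaps (*k*) | Shift at *d* = 1 | Share of SE | Shift at *d* = 0.5 | Share of SE |
|---|---|---|---|---|
| 1 | 0.10 SD | 32% | 0.05 SD | 16% |
| 2 | 0.20 SD | 63% | 0.10 SD | 32% |
| 3 | 0.30 SD | 95% | 0.15 SD | 47% |

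At *d* = 1, about three swaps in the same direction amount to one standard error. The table shows how little it takes to move an estimate from 40 people. It says nothing about how likely any swap is.

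**The case against.** The strongest reply is that the decisive text is missing from the copy reviewed, not shown to be missing from the plan. The script is the natural home for rules on opening order, identifiers and logging. This stands in full: nobody can say from these documents that such rules are absent.

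Other parts of the reply also carry weight:

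- The envelopes are sealed, marked only with a number, kept separate by sex and filled from a biostatistician's list. If they are also opaque, held independently and opened in order, they can conceal allocation well. Numbered envelopes could also in principle be reconciled against the list and the REDCap consent records. A reader might infer that swaps could never be detected; the documents do not show that.
- A reader might infer that one person screens, consents, holds the envelopes and opens them. The documents name a role, use the plural elsewhere (section 8), and are silent on custody.
- Participants are already identified in REDCap through consent, and are asked to complete the baseline surveys before the training visit (4a). Much of the ordering one would want is therefore planned already.
- The remote-visit point does not apply to those randomised in person.
- The trial's aim is feasibility and acceptability. Its feasibility outcomes are descriptive, and no hypothesis test is specified for the patient-reported outcomes.

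These points limit the conclusion to a gap in assurance. They do not restore the inference that section 4c draws, because who generates the list still does not determine how assignments are released. The argument that a sentence on envelope handling would be enough is fair, but central release gives stronger concealment than envelopes opened at the site, whatever the script says.

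**Conclusion.** The concern holds in a limited form. The stated lack of staff control rests on sequence generation alone, while release is in the hands of the research assistant role, using sealed, pre-filled envelopes. Concealment is not assured by the procedure as shown. A reader might go further and conclude that concealment fails, or that staff do control allocation. The documents do not support that, given the missing script and the unstated custody.

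The consequence is modest. It falls on the between-group patient-reported differences and on any by-arm attendance or retention comparison. The figure of 0.10 SD per swap against a standard error of 0.316 SD is illustrative and depends on 20 per arm, a 1 SD gap and same-direction swaps, all assumed. The change is worth making because it is cheap and leaves the sample size of 40, the equal allocation and the sex stratification as they are.

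**What to change.** Keep the biostatistician's sex-stratified list, but load it into REDCap and release each assignment there, with user and time stamp, only after eligibility, sex and completed baseline have been saved. REDCap already handles consent (3c), surveys (4a, 4d), attendance (4d) and adverse event forms (8a), so no new system is introduced. The documents do not show that its randomisation function is available at this site. If it is not, the biostatistician releases each assignment on request after the participant has been registered. Section 4c should then rest its assurance on the release step and say who holds the list.

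The cost is a short build, or some turnaround time under the fallback, plus a protocol sentence. A working connection is needed at the visit; the remote visit needs one anyway, and the in-person randomisation would need one too.

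If envelopes are kept, the protocol should at least state that they are opaque, held by someone who neither screens nor consents, opened in strict order within sex, marked with identifier and date before opening, and reconciled to a log. If the script already says this, it should be cited in section 4c. Neither route settles predictability from block size, which the text does not state. Any blocking scheme should be documented where staff who enrol cannot see it.

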Knee Osteoarthritis (**OA**) is a highly prevalent condition, ¹⁻³ which poses a huge burden on the healthcare system. Exercise has been used as the first-line treatment for knee OA.^{4,5} However, people with psychological factors such as high pain catastrophizing, low-self-efficacy, low mindfulness trait, fear of pain, and mood disturbances tend to have poor response to exercise treatments.⁶⁻¹² Additionally, neurobiological mechanisms such as central sensitization, characterized by hypersensitivity to pain stimulus due to abnormal neural signalling, ¹³ in people with chronic pain has been associated with poor response to exercise. ¹⁴ Mindfulness is a practice of non-judgment and moment-to-moment awareness. ¹⁵ There is an accumulating body of evidence that suggests that mindfulness can improve psychological factors such as pain catastrophizing, fear of movement, and pain hypersensitivity – factors that may be associated with poor response to exercise. Taking these evidence together, we posit that an intervention developed by combining mindfulness with traditional exercise treatments may increase the effectiveness of exercise alone. Before we test the effectiveness of such an intervention, we need to establish the intervention feasibility and acceptability. ¹⁶ Therefore, the goal of this randomized controlled trial (RCT) is to determine the **feasibility** and **acceptability** of a mindful exercise program compared to exercise in people with knee OA.

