The Telehealth Exercise and Mindfulness for Pain in Osteoarthritis (TEMPO) is a longitudinal, parallel arm, 14-week clinical trial that will investigate the feasibility of an 8-week telehealth-delivered, group-based mindful exercise program. For this, forty people with knee OA will be recruited. These participants will be randomly assigned to either an 8-week mindful exercise program OR an 8-week exercise only program. Both programs will include weekly sessions (n=8 total) that will be delivered in a group setting (n=10 per group) by real-time videoconferencing (HIPAA-protected Zoom). Before the start of the interventions, all participants will attend an individualized remote randomization and telehealth training session where participant's group assignment will be randomized, and instructions for home set up and requirements for the remote sessions will be discussed. Participants will be administered surveys on pain, function, and mood before the start of the intervention (week 0), at post-intervention (week 8), and 6-weeks after the end of the interventions (week-14). Participants will be given an option to participate in two in-person visits at Boston University before the start (baseline visit) and at the end of the interventions (post-intervention visit). During these optional in-person visits, the participant's function, muscle strength, sensitivity to painful stimulus, and brain activity will be collected. Brain activity will be measured using functional near-infrared spectroscopy (fNIRS). At the end of the 8-week interventions, participants in the mindful exercise group will be invited to participate in individual interviews. The interviews will be conducted over Zoom to understand participant's perspective related to acceptability of the mindful exercise intervention

2b. Schedule of Visits

Figure 1 is a schematic diagram depicting the study flow. A list of measurements collected at each visit is shown below in **Table 1**. Apart from the research and intervention visits, the various timepoints of email and telephone contact with the participants in the study is shown in **Table 2**.

[figure not shown]

Figure 1. Study flow for participants in the study

 Table 1. Schedule of Study Visits and Measurements

Week	~ -3	-2	-1	0	1	2	3	4	5	6	7	8	9-13	14
Visits			BV-R	RTT								W8-R		W14-R
Telephone Screening	X													
Consent and Enrollment	X													
Randomization				X										
Exercise Program					X	X	X	X	X	X	X	X		

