At the end of the 8-week interventions, participants from the mindful exercise intervention will be invited for individual interviews. The interviews will be conducted over Zoom by a professor who is an expert in qualitative methods and who was not involved in any other study procedures. The interview guide will be theoretically informed based on the Theoretical Framework of Acceptability(1). The interviews will be audio-recorded on Zoom and transcribed verbatim and de-identified by GMR transcription services in Boston.

5. Interventions Description, Overview, Objectives

5a. General Overview

Two days before the first intervention session, participants will receive a reminder email informing them of the date, time, and zoom link of the intervention session. This information will also be provided in the manual given to them at the baseline visit. One day before the intervention session, participants will receive a call from the research assistant reminding them of the first intervention session.

Participants in both groups will receive 8 telehealth, group-based, supervised intervention sessions. Participants in the exercise group will receive evidence-based strengthening and neuromuscular exercises for the knee for 12-weeks. Participants in the mindful exercise group will receive the same exercises but they will be trained on performing the exercises mindfully. The interventions will be conducted in two waves.

5b. Interventions

Interventions will be delivered in a group setting in two waves over 8-weeks. Once at least 12 people are recruited, interventions for wave 1 will commence. Recruitment and randomization processes will be ongoing while interventions for wave 1 participants are in progress. Once 40 participants are randomized, recruitment will cease and the interventions for the second wave of participants will commence.

[figure not shown]
Interventions in both mindful exercise and exercise groups will be delivered in a group setting via HIPAA-protected Zoom videoconferencing software. Along with the interventions below, participants in both groups will receive educational materials each week via email (Table 5), a program manual that contained information about study tasks and interventions, and a set of resistance bands and a step-up platform with adjustable height. After the end of the 8-week interventions, participants were asked to continue to practice on their own for another 6 weeks.

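### Acceptability interviews are timed only at the end of the 8 weeks, so the views of people who stop the mindful program early may be under-represented

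*Combined protocol and SAP*

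**What the plan says.** The background section states that, before effectiveness is tested, "we need to establish the intervention feasibility and acceptability". The study overview gives the purpose of the interviews: "The interviews will be conducted over Zoom to understand participant's perspective related to acceptability of the mindful exercise intervention". Section 4g adds that the guide draws on a published framework of acceptability.

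The timing is the same wherever it is given:

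- Study overview: "At the end of the 8-week interventions, participants in the mindful exercise group will be invited to participate in individual interviews".
- Section 4, opening paragraph: "individual interviews at week 8 only for participants in the mindful exercise group".
- Section 4g: "At the end of the 8-week interventions, participants from the mindful exercise intervention will be invited for individual interviews".
- Table 1 has one entry for the interviews, at week 8, and Table 4 places them at the end of treatment.

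The other planned source of participants' opinions is the set of feedback and satisfaction surveys. Section 4d gives their trigger: "The completion of the 8th session will trigger the ASI for the post-intervention remote surveys". No other trigger is described.

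The weekly surveys (section 4f) run from week 1 to week 14 for everyone. They cover activity pain, home exercise, physical activity and medication. For the mindful arm, "additional questions related to mindfulness and mindful exercise log will be included".

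The statistical analysis plan (section 7) reports attendance and retention descriptively and participant feedback in aggregate. It does not mention the interviews.

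**The concern.** People who leave a program partway through because of the program itself are well placed to say what made it hard to accept. Here the question is pointed. The mindful sessions last about 2 hours against 1 hour for exercise alone, and participants are also advised to practise mindfulness for at least 20 minutes a day (sections 5b.1 and 5b.2).

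The plan has no step that gathers the views of such people near the time they stop. Both routes to their opinions come at the end of the program, and one of them depends on completing the last session. If those who stop are harder to recruit to an interview weeks later, the acceptability account will lean towards those who stayed, and the reasons for stopping may go unrecorded. Those reasons are what the designers of the next trial would need, and they are hard to recover afterwards.

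**Working it through.** The plan states no dropout rate, interview uptake or target number of interviews, so there is no figure of its own to reproduce. Two things can be checked: the delay, which follows from the schedule, and the make-up of the interviewees, which needs assumptions.

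**Size of the arm.** The overview gives 40 participants and section 4c gives each an equal chance of either group, so about 20 are in the mindful arm. This agrees with 10 per group × 2 arms × 2 waves = 40.

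**Delay.** Sessions are weekly in weeks 1 to 8 (Table 1). Someone whose last session is number *k* is first invited about 8 − *k* weeks later. For *k* = 1 to 7 this is 7, 6, 5, 4, 3, 2 and 1 weeks.

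**Make-up of the interviewees.** Let *d* be the number of the 20 who stop, *u* the interview uptake among those who stay and *r* the uptake among those who stop. All three are assumed.

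Share of interviewees who had stopped = *d·r* / [*d·r* + (20 − *d*)·*u*]

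With *u* = 80%:

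| *d* | share of arm | *r* = 25% | *r* = 50% | *r* = 80% (equal) |
|---|---|---|---|---|
| 2 | 10% | 0.5/14.9 = 3% | 1/15.4 = 6% | 10% |
| 4 | 20% | 1/13.8 = 7% | 2/14.8 = 14% | 20% |
| 6 | 30% | 1.5/12.7 = 12% | 3/14.2 = 21% | 30% |

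With *u* = 90%, the case *d* = 4 and *r* = 25% gives 1/15.4 = 6%, so the result is not sensitive to *u*. At equal uptake the share among interviewees matches the share of the arm, and there is no under-representation.

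**Chance that nobody who stopped is interviewed.** For qualitative work this matters more than the share. If people decide independently, the chance is (1 − *r*)^*d*. For *d* = 4 it is 0.75⁴ = 32% at *r* = 25% and 0.5⁴ = 6% at *r* = 50%. For *d* = 2 it is 56% and 25%; for *d* = 6 it is 18% and 2%.

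**The case against.** The strongest reply is that nobody is left out. Section 4g invites participants from the mindful arm, not completers. The interview is remote and paid. Attendance is tracked weekly, and the weekly surveys go out by email with automated reminders to week 14, so some contact may continue after a person stops attending. This stands. It makes lower uptake among those who stop less certain, and it rules out any claim that they are excluded.

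A reader might infer that the acceptability conclusion will rest mainly on those who stayed, and that this shows bias. The documents do not support that. If 16 of 20 stay, a perfectly representative set of interviewees is already 80% stayers. The issue is whether those who stop fall below their share of the arm, and no stated rate settles it.

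A reader might also want the effect as percentage points of acceptability. Suppose further that 90% of stayers and 30% of those who stop find the program acceptable. Then *d* = 4, *u* = 80% and *r* = 25% give (12.8 × 0.9 + 1 × 0.3)/13.8 = 86% among interviewees, against (16 × 0.9 + 4 × 0.3)/20 = 78% in the arm. For *d* from 2 to 6 and *r* from 25% to 50% the gap is 2 to 11 points. It comes entirely from the assumed unequal uptake and is 0 when uptake is equal. Neither section 4g nor section 7 plans to estimate a percentage acceptable from the interviews, so these figures should not be read as a bias in a planned result.

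Attendance and home adherence would make heavy drop-off visible beside favourable interviews. That is true, but they record behaviour, not views or reasons. Retention, as section 7 defines it, is itself measured by completing the post-intervention surveys.

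Finally, the survey trigger could be read as the group's eighth session being held, not the individual completing it. Section 4d does not say, which is why the surveys may be missed, not that they will be.

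**Conclusion.** The point holds as a gap in the plan, not as a demonstrated bias. The interviews are fixed at the end of the program, and the only stated trigger for the feedback surveys is completion of session 8. No step secures the views of people who stop while those views are fresh. The delay of 1 to 7 weeks follows from the schedule. The degree of under-representation cannot be derived from the documents. It is nil at equal uptake; in the illustrative case of 4 of 20 stopping with 25% of them reached, it is about 7% of interviewees against 20% of the arm. Randomisation and the planned between-group comparisons are unaffected. Because acceptability is one of two stated goals and the remedy is cheap, the change should be made before interviews begin.

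**What to change.** - **Timing.** In the study overview, section 4, Table 1, Table 4 and section 4g, state that everyone randomised to the mindful arm is invited regardless of attendance, at week 8 or within about two weeks of stopping, whichever comes first. All five places must change together, or the protocol will contradict itself. Interviewer, guide and payment stay the same.
- **Trigger.** Define stopping, for this purpose only, from the weekly attendance survey. For example, the participant says they are stopping, or misses a pre-set number of consecutive sessions. Since section 4g keeps the interviewer apart from other study procedures, the research assistant should notify the interviewer.
- **Surveys.** In section 4d, send the feedback and satisfaction surveys at calendar week 8 to those who do not complete session 8.
- **Reporting.** In section 7, report the numbers invited and interviewed by attendance, and summarise the themes of those who stopped separately.

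The cost is short edits in these places and one added survey rule. The interviewer must be available during each wave, and a few interviews will fall at a different time from the rest. The number of interviews offered does not change. For someone whose last session is 6 or 7 the earlier invitation gains little; the benefit is for those who stop sooner.
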